#### 12.4.4. Secondary Analyses

Treatment comparisons between ATI-1777 and vehicle for each of the continuous efficacy endpoints that are conducted over time (change in IGA, BSA, and PP-NRS) will be analyzed using a similar model as described for the primary endpoint. Treatment comparisons will be made for each post-baseline scheduled visit utilizing the analysis window scheme described in [Section 10.1.1](#). Change from baseline is calculated as described in [section 10.1.3](#).

Treatment group comparisons for categorical efficacy endpoints (IGA response, EASI-50, EASI-75, and EASI-90) that are conducted over time will employ a logistic regression model fit at each scheduled visit separately, where appropriate. The logistic regression model will include treatment group and baseline severity of AD as a factor, and the baseline value as a covariate. Model-based point estimates for the treatment proportions will be provided as well as model-based differences and corresponding symmetric 90% confidence intervals and one-sided p-values. If the Logistic model will not converge or if there is strong collinearity between the baseline EASI score and the baseline severity of AD, one or both of the covariates may be excluded from the secondary analysis.

The secondary efficacy endpoints are

- Percent change from baseline in EASI score at each study visit
- Proportion of patients achieving an IGA score of 0 to 1 combined with an improvement of 2 or more points from baseline within 4 weeks of the start of treatment
- Proportions of patients who achieve EASI-50, EASI-75, and EASI-90 within 4 weeks of the start of treatment
- Change from baseline in IGA score at each study visit
- Change from baseline in BSA at each study visit
- Change from baseline in PP-NRS score over time

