##### 12.4.4.1. EASI, EASI-50, EASI-75 and EASI-90

The analysis of percent change from baseline in EASI score at each visit for FAS will be in the same model as the primary efficacy analysis. The estimates at the timepoint other than Week 4 will be considered as secondary endpoints.

EASI-50, EASI-75 and EASI-90 are the proportions of patients achieve 50%, 75%, 90% improvement in EASI score respectively within 4 weeks of the start of the treatment. The follow is an example of EASI-50 definition.

EASI-50 = “YES” If (EASI score at Day 28 – baseline EASI)/baseline EASI  $\geq 50\%$

The follow SAS code is an example for the analysis of EASI-50 at Day 28.

```

proc logistic data= datain;
  class treatment baseline ADseverity;
  model EASI_50 = baseline EASI treatment baseline ADseverity / expb;
  oddsratio treatment;
  lsmeans treatment / e diff oddsratio cl adjust = bon;
run;

```

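### The example PROC LOGISTIC code in SAP 12.4.4.1 does not implement the responder analysis that SAP 12.4.4 and protocol 9.4.5 specify

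*SAP*

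**What the plan says.** **The specification.** SAP 12.4.4 covers IGA response, EASI-50, EASI-75 and EASI-90 and promises: "Model-based point estimates for the treatment proportions will be provided as well as model-based differences and corresponding symmetric 90% confidence intervals and one-sided p-values". Protocol 9.4.5 makes the same commitment, apart from the word for symmetry, and fixes the direction of every efficacy test as superiority of ATI-1777 over vehicle. SAP 12 sets the level at one-sided 5%.

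**The responder variable.** SAP 12.4.4.1 begins the derivation "EASI-50 = “YES” If (EASI score at Day 28" and continues with the change divided by baseline being at least 50%. Only the YES level is named.

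**The code.** SAP 12.4.4.1 then gives a short block, labelled an example and written for the Day 28 analysis of EASI-50. Line by line:

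- The procedure is called with "proc logistic data= datain", which sets neither a response order nor a confidence level.
- The factors are declared by "class treatment baseline ADseverity", without a parameterisation option.
- The regression itself is "model EASI_50 = baseline EASI treatment baseline ADseverity / expb", where the response carries no event option.
- An odds ratio is requested through "oddsratio treatment", again at the default level.
- The adjusted means come from "lsmeans treatment / e diff oddsratio cl adjust = bon", which has no inverse-link option.

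Blanks inside variable names may come from reading the PDF and are not counted here. By comparison, the code for the primary model in SAP 12.4.3.4 does set alpha=0.10.

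**The concern.** The block is the only worked code for the responder analyses, which SAP 12.4 requires in both the FAS and the PP set. Four things the specification needs are absent: a named event level, a CLASS parameterisation under which LSMEANS can run, a step from log-odds to proportions and their difference, and 90% limits with a one-sided p-value. Neither document says how the difference in proportions or its interval is to be computed, so the gap in the code is not filled elsewhere.

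The direction and scale of the reported responder effects are at stake. An odds ratio for non-response can be mistaken for one for response. The planned proportions and differences would also have to come from a method chosen later, outside the plan.

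**Working it through.** The plan states no figure on this point, so the check sets the code against the specification and then sizes the effect. Three assumptions come from outside the documents: PROC LOGISTIC models the first ordered response level by default, its default CLASS coding is effect coding, and LSMEANS in this procedure needs GLM coding.

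**1. Event level.** The code has no EVENT=, DESCENDING, REF= or ORDER= on the response. NO sorts before YES, N before Y, 0 before 1. Under any of these codings the fitted probability is that of non-response. A coding of 1 = yes, 2 = no would not invert.

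**2. Size, simple illustration (assumed rates, ratio taken as ATI-1777 over vehicle).**
- Modelling YES: (0.6/0.4)/(0.2/0.8) = 6.0.
- Modelling NO: 1/6.0 = 0.17.

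**3. Size, planning inputs.** SAP 8.3 gives mean improvements of 65 and 20 and a spread of 38.3. Read as an SD with 17 per arm, the noncentrality is 45/(38.3 × √(2/17)) = 3.43 on 32 df. One-sided 5% power is then 95.61%, against 95.6% stated, so 38.3 acts as an SD. Assuming normality, EASI-50 rates are 1 − Φ((50 − 65)/38.3) = 65.2% and 1 − Φ((50 − 20)/38.3) = 21.7%.

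| Endpoint | ATI-1777 v vehicle | OR, modelling YES | OR, modelling NO |
|---|---|---|---|
| EASI-50 | 65.2% v 21.7% | 6.78 | 0.147 |
| EASI-75 | 39.7% v 7.5% | 8.06 | 0.124 |
| EASI-90 | 25.7% v 3.4% | 9.89 | 0.101 |

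**4. Interaction with the derivation.** SAP 10.1.3 defines change as post-baseline minus baseline, so improvement is negative. Taken literally, a change of at least +50% flags worsening. On the same inputs the literal YES rates are Φ((−50 − 65)/38.3) = 0.13% on ATI-1777 and Φ((−50 − 20)/38.3) = 3.4% on vehicle. Modelling NO then gives an odds ratio of about 26, above 1. The two reversals offset each other in direction, and correcting only one exposes the other.

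**5. Scale.** The CLASS statement has no PARAM=GLM, so LSMEANS would not be expected to run; the ODDSRATIO statement still would. If LSMEANS did run, it has no ILINK and would give logits. An invented dataset shows the difference (25 per arm, 16 v 5 responders, baseline score and severity in the model, response coded as improvement):
- Modelling NO, LS-means are −0.18 and 1.82 on the logit scale, difference −2.00.
- Modelling YES and standardising over patients gives 63.6% and 20.1%, difference 43.5 points.
- Modelling YES and back-transforming the LS-means gives 54.5% and 13.9%, difference 40.6 points.

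ILINK alone would supply the back-transformed proportions but not their difference or its interval. The last two results also differ, so the method has to be named.

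**6. Limits and p-values.** The code has no alpha=0.10, so limits default to 95%, and no one-sided p-value is requested. In the same dataset the two-sided p is 0.0026 whichever level is modelled. The upper-tail p is 0.0013 when YES is modelled and 0.9987 when NO is modelled.

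**The case against.** The strongest reply is that this is example code and the prose governs. SAP 12.4.4 and protocol 9.4.5 still commit to the right outputs, and a programmer would be expected to add what is missing. That stands: a reader might infer that the proportions and differences have been dropped from the plan, and the documents do not support it. The mismatch is between code and text. Nor do they call the block the template for IGA response; SAP 12.4.4.2 says only that logistic regression will be used.

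A reader might also infer that, run exactly as written, the code makes a beneficial drug show an odds ratio below 1. That is not established. It needs a NO/YES or 0/1 coding that the SAP does not give, the assumed software default, and a derivation read as improvement; on the literal derivation the direction is the opposite (step 4).

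Nor should one say that the code prints a logit difference such as ln(0.17) = −1.79 in the simple illustration. Without GLM coding LSMEANS would not be expected to print anything.

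A one-sided p-value in the wrong tail would need a further mistake. The code prints two-sided values, and the text fixes the direction of the test. Responder counts and percentages, which SAP 12 provides for categorical variables, would also make an inverted ratio visible.

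None of this removes the central point. Whatever the coding, the block yields no response proportion, difference in proportions, 90% interval or one-sided p-value.

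**Conclusion.** The example code does not implement the specified responder analysis. The missing proportions, difference, 90% interval and one-sided p-value do not depend on how the response is coded. The inversion is conditional: with NO/YES or 0/1 coding, the standard default and the responder definition read as improvement, the reported odds ratio is the reciprocal of the intended one. That is 0.17 for 6.0 at 60% v 20%, or 0.147 for 6.78 on the planning inputs under normality.

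Only secondary responder endpoints in a Phase 2a study are affected, and the primary mixed model is not. It is a should-fix, to be made before unblinding.

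**What to change.** Replace the block in SAP 12.4.4.1 with code that matches SAP 12.4.4:

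- `model EASI_50(event='YES') = ...`, with both levels of the response stated.
- `class treatment(ref='Vehicle') baseline_ADseverity / param=glm`.
- `alpha=0.10` for every interval requested.
- Proportions and their difference by standardisation: predict each patient in the analysis set under both arms, average within arm, and subtract. Use the FAS for the FAS analysis and the PP set for the PP analysis. Give a symmetric delta-method 90% interval.
- A one-sided p-value defined in the direction of superiority of ATI-1777.
- The same code for EASI-75, EASI-90 and IGA response.

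Correct the sign of the EASI-50 derivation in the same edit, so that YES means an improvement of at least 50%. Removing the Bonferroni option is tidy-up only, since with two arms there is one comparison.

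The cost is a few lines of SAP text and code, with no change to the data collected or to the protocol.

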#### 12.4.4.2. Investigator's Global Assessment (IGA)

The IGA is the investigator's assessment of the overall appearance of the lesions at a particular point in time. At every study visit, the investigator will assess the IGA using the scale in [Table 6](#) and report the one score that best describes the overall appearance of the lesions. It is not necessary that all characteristics under Morphological Description be present. In indeterminate cases, please use extent to differentiate between scores. The investigator or qualified designee will enter the score into the eCRF. Whenever possible, the same individual should conduct the evaluation at each visit.

**Table 6 IGA Scoring**

| Score            | Morphological Description   |
|------------------|---|
| 0 - Clear        | No inflammatory signs of atopic dermatitis (no erythema, no induration/papulation, no lichenification, no oozing/crusting). Post-inflammatory hyperpigmentation and/or hypopigmentation may be present. |
| 1 - Almost clear | Barely perceptible erythema, barely perceptible induration/papulation, and/or minimal lichenification. No oozing or crusting.   |
| 2 - Mild         | Slight but definite erythema (pink), slight but definite induration/papulation, and/or slight but definite lichenification. No oozing or crusting.  |
| 3 - Moderate     | Clearly perceptible erythema (dull red), clearly perceptible induration/papulation, and/or clearly perceptible lichenification. Oozing and crusting may be present.                                     |
| 4 - Severe       | Marked erythema (deep or bright red), marked induration/papulation, and/or marked lichenification. Disease is widespread in extent. Oozing or crusting may be present.                                  |

IGA = Investigator's Global Assessment

The change from baseline in IGA score at each study visit is analyzed using similar MMRM model as the primary efficacy endpoint except the baseline IGA score will be included as a covariate.

The patient achieves an IGA score of 0 or 1 combined with an improvement of 2 or more points from baseline within 4 weeks of the start of treatment is analyzed as categorical variable using logistic regression.

#### 12.4.4.3. Body Surface Area (BSA)

The total percentage of the patient's AD-affected BSA will be estimated by the investigator or designee using the handprint method, which estimates that the area of a patient's full handprint (fingers and thumbs together) constitutes 1% of their total BSA.

The BSA should be calculated for the EASI score using Regional Percentage Estimates as described in the study training video.

Whenever possible, the same evaluator should perform the estimation at each study visit. If new areas of AD develop while the patient is on the study, these new areas will not be assessed.

BSA results and corresponding change from study baseline values will be summarized at each time point using descriptive statistics by treatment group. The change from baseline in AD BSA at each study visit is analyzed using similar MMRM model as the primary efficacy endpoint.

#### 12.4.4.4. Peak Pruritus Numerical Rating Scale (PP-NRS)

The PP-NRS ([Yosipovitch et al 2019](#)) is a single patient-reported item designed to measure peak pruritus, or ‘worst’ itch, over the previous 24 hours based on the following question: ‘On a scale of 0 to 10, with 0 being “no itch” and 10 being “worst itch imaginable,” how would you rate your itch at the worst moment during the previous 24 hours?’.

Prior to study medication application on Day 1, the study coordinator should show the PP-NRS scale to the patient, explain the scale and ask the patient to indicate which integer best describes the worst pruritus the subject experienced for their AD over the previous 24 hours.

The patient will complete this assessment and record in their diary each morning before applying study medication during the Treatment Period.

The patient will report the diary rating to site staff at each visit, who will enter it into the patient’s source documents and eCRF.

The PP-NRS score on Day 1 prior to study medication application is the baseline. The PP-NRS scores just prior to study medication application on Day 8, Day 15 and Day 28 will be flagged and used in the efficacy analysis. PP-NRS results and corresponding change from study baseline values will be summarized at each time point using descriptive statistics by treatment group. The change from baseline in PP-NRS is analyzed using similar MMRM model as the primary efficacy endpoint.

All PP-NRS score data will be presented in a data listing, the values included in the efficacy analysis will be flagged.

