3.2 Secondary Endpoints

The secondary endpoints are:

- Percent change from baseline in EASI score at each study visit
- Proportion of patients achieving an IGA score of 0 to 1 combined with an improvement of 2 or more points from baseline within 4 weeks of the start of treatment
- Proportions of patients who achieve 50%, 75%, and 90% improvement in EASI score (EASI-50, EASI-75, and EASI-90, respectively) within 4 weeks of the start of treatment
- Change from baseline in IGA score at each study visit
- Change from baseline in AD BSA at each study visit
- Change from baseline in PP-NRS score over time

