A total of approximately 50 patients who meet all the entry criteria will be randomized on Day 1 via an interactive voice/web response system (IXRS) to ATI-1777 or vehicle treatment in a 1:1 ratio. Patients will be stratified at randomization by severity of AD (moderate versus severe). The study is randomized and double-blinded with regard to ATI-1777 and vehicle in order to prevent bias in treatment allocation and in the assessment of treatment effect. The investigator, site personnel, the sponsor, and their representatives involved in monitoring and conducting the study, and the patients will be blinded to the study medication administered. See [Section 7.3](#) for further details on the

method of assigning patients to the treatment groups, and [Section 7.2](#) for details on access to the treatment codes in the event of emergency unblinding.

During the Treatment Period, patients will apply study drug (ATI-1777 topical solution 2.0% w/w or vehicle) twice daily for 28 days to target areas affected by AD. Patients will be trained by site personnel on how to appropriately apply the study medication. See [Section 7.4](#) for further details on the dose and administration of ATI-1777 and vehicle.

On Day 1 of the study, patients will apply drug in the clinic. The application site will be assessed for serious or severe local AEs prior to discharge from the clinic. Subjects will be informed to contact the site if a severe or serious event occurs. Subjects will be asked to pay particular attention to any events in the first 24 hours after drug administration.

During treatment, patients will attend weekly study visits. At the study visits, AE collection, physical examinations, clinical disease assessments (EASI, IGA, BSA, and PP-NRS), vital sign assessments, PK evaluations, and clinical laboratory evaluations will be performed as detailed in the Schedule of Events (Table 1). Patients will complete a daily diary recording their dose administration and PP-NRS itch score during the study.

For all study participants, blood samples will be collected for PK analysis according to the sparse sampling approach described in [Section 6.4](#).

Participants who discontinue study medication earlier than Day 28 will have an Early Termination (ET) Visit at the time of study medication discontinuation and will return for a PTFU Visit, 2 weeks (± 3 days) after the Day 28/ET Visit (see [Table 1](#)).

4.1.3 *Follow-up Period*

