The PP-NRS ([Yosipovitch et al 2019](#)) is a single patient-reported item designed to measure peak pruritus, or 'worst' itch, over the previous 24 hours based on the following question: 'On a scale of 0 to 10, with 0 being "no itch" and 10 being "worst itch imaginable," how would you rate your itch at the worst moment during the previous 24 hours?'.

Prior to study medication application on Day 1, the study coordinator should show the PP-NRS scale to the patient, explain the scale and ask the patient to indicate which integer best describes the worst pruritus the subject experienced for their AD over the previous 24 hours.

The patient will complete this assessment and record in their diary each morning before applying study medication during the Treatment Period.

The patient will report the diary rating to site staff at each visit, who will enter it into the patient's source documents and eCRF.

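### PP-NRS is scored every morning, but the SAP analyses three single post-baseline days and so gives up precision that a 7-day mean of the diary scores would recover

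*SAP*

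**What the plan says.** **Collection.** Protocol 6.2.4, repeated in SAP 12.4.4.4, sets up a daily diary: "The patient will complete this assessment and record in their diary each morning before applying study medication during the Treatment Period". Each score covers the preceding 24 hours. Protocol 4.1.2 has study drug applied "twice daily for 28 days to target areas affected by AD", so there are about 28 diary mornings per patient.

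**Analysis.** SAP 12.4.4.4 fixes the baseline as one score: "The PP-NRS score on Day 1 prior to study medication application is the baseline". For follow-up, the efficacy analysis takes one score per visit: "PP-NRS scores just prior to study medication application on Day 8, Day 15 and Day 28 will be flagged and used". The change from baseline goes into an MMRM modelled on the primary analysis. The other scores appear only in a listing: "All PP-NRS score data will be presented in a data listing, the values included in the efficacy analysis will be flagged". No weekly mean, model for the daily data or sensitivity analysis on them is planned. The window rule in SAP 10.1.1 covers PP-NRS, and it too picks one value, the one nearest the target day.

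**Endpoint wording.** Protocol 3.2 lists "Change from baseline in PP-NRS score over time". The table in SAP 9.1 words the endpoint per study visit, and SAP 12.4.4 keeps the protocol's wording.

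**Covariate.** SAP 9.3 names continuous baseline scores for EASI, BSA and IGA, but not for PP-NRS.

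**The concern.** A score that describes one 24-hour period carries that day's fluctuation as well as the patient's underlying itch level. The plan already asks patients for a score on every day around each visit, yet takes a single one. If itch varies at all from day to day within a patient, the treatment comparison has a larger standard error than the diary data would allow.

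PP-NRS is the only efficacy endpoint that the patient reports; EASI, IGA and BSA are rated by site assessors. With about 50 patients enrolled, a real itch effect is easier to miss if avoidable noise stays in the analysis.

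**Working it through.** **The plan's own figure.** The only stated power is for EASI (SAP 8.3, Protocol 9.3). With 17 per arm, a difference of 65 − 20 = 45 and 38.3 read as an SD, the SE is 38.3 × √(2/17) = 13.14 and the noncentrality is 45/13.14 = 3.43. A one-sided 5% t-test on 32 df then has 95.6% power, as stated. This confirms the EASI calculation but says nothing about PP-NRS, for which the documents give no SD, effect size, correlation or power.

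**Scores used.** Of 28 mornings, Day 1 is the baseline, which leaves 27. Three are analysed (3/27 = 11%) and 24 are not (24/27 = 89%).

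**Model for precision.** Assumptions, none of them from the documents:
- The variance of a single-day score is 1, split into ICC (stable within the week) and 1 − ICC (day-to-day).
- Daily errors are independent.
- The single Day 1 score is the covariate.
- r is the correlation between true baseline and true Week 4 itch.

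Baseline-adjusted variance, single day: 1 − (ICC·r)².

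Baseline-adjusted variance, 7-day mean: ICC + (1 − ICC)/7 − (ICC·r)².

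With r = 0.5:

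| ICC | single day | 7-day mean | SE ratio (mean/single) | fall in SE | sample-size ratio |
|---|---|---|---|---|---|
| 0.5 | 0.9375 | 0.5089 | 0.737 | 26% | 1.84 |
| 0.7 | 0.8775 | 0.6204 | 0.841 | 16% | 1.42 |
| 0.8 | 0.8400 | 0.6686 | 0.892 | 11% | 1.26 |
| 0.9 | 0.7975 | 0.7118 | 0.945 | 6% | 1.12 |

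Moving r from 0.3 to 0.7 changes little: the fall is 25–28% at ICC 0.5, 15–19% at 0.7 and 5–7% at 0.9.

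**Less favourable cases**, at ICC 0.5, 0.7 and 0.9:
- AR(1) daily errors with correlation 0.5, no baseline adjustment: the single-day SE is 1.218, 1.115 and 1.034 times the 7-day SE, a fall of 18%, 10% and 3%.
- Unadjusted change from the single Day 1 score, independent errors, r = 0.5: ratios 1.183, 1.117 and 1.041, a fall of 15%, 10% and 4%. The gain is smaller because the baseline noise remains.

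**In scale points.** With an assumed single-day SD of 2.5, 25 per arm and r = 0.5, the SE of the treatment difference goes from 0.69 to 0.50 (ICC 0.5), 0.66 to 0.56 (0.7) and 0.63 to 0.60 (0.9).

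**Other visits in the MMRM.** With complete or LOCF-filled data, Days 8 and 15 do not stand in for the unused scores around Week 4, so the model does not recover the loss.

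**Dilution.** A weekly mean is worse if the effect is still building and the mean captures too little of it. Break-even is the SE ratio: at r = 0.5 the mean must keep more than about 74%, 84% or 94% of the single-day effect at ICC 0.5, 0.7 or 0.9.

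**The case against.** The strongest reply is that this is one unpowered secondary endpoint in a Phase 2a study without multiplicity control, that the estimate stays unbiased and the test valid, and that the gain depends on variance components the documents do not contain. All of that stands. It limits the weight of the point but not its direction: any day-to-day variance above zero makes the single-day score the less precise choice.

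It is also fair to say that a weekly mean answers a slightly different question, and that the data may not be in the database. SAP 12.4.4.4 says "The patient will report the diary rating to site staff at each visit", in the singular. The planned listing of all scores implies that every diary day is entered but does not settle it.

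Three stronger readings are tempting, and the documents do not support them:
- **A missed diary on a named day leads straight to LOCF although neighbouring days were recorded.** SAP 10.1.1 and Table 2 apply analysis windows to PP-NRS, and SAP 12.4.4 uses that scheme for these comparisons. A recorded adjacent day could be selected before any carry-forward.
- **The protocol's endpoint wording requires the daily data.** Protocol 9.4.5 specifies comparisons at each scheduled post-baseline visit and names PP-NRS. Footnote 8 to the Schedule of Events has it assessed at study visits. The SAP's visit-based analysis is consistent with both.
- **The gain could be much larger than 26%.** Bigger figures come from setting the observed single-day baseline-to-Week-4 correlation as high as the within-week correlation, for example both 0.5. True baseline and Week 4 itch would then have to correlate at 0.5/0.5 = 1, which is not credible across four weeks of treatment.

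**Conclusion.** The point holds as a matter of efficiency. About 24 of 28 diary scores per patient are collected and listed but play no part in the efficacy analysis, and no averaged or daily analysis is planned. The loss is precision only.

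Under independent daily errors, with the Day 1 score as covariate and r = 0.5, a 7-day mean would lower the standard error by about 6% to 26% for ICC 0.9 down to 0.5. With autocorrelated errors or without baseline adjustment, the fall is about 3% to 18%. These ranges are illustrations; the documents cannot narrow them. The change is worth making because the patient burden is already there and the derivation is simple.

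**What to change.** In SAP 12.4.4.4:

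1. Define the PP-NRS value at each visit as the mean of the available post-baseline diary scores from the 7 mornings up to and including the visit day. Exclude the Day 1 pre-dose score and any morning at or before the preceding scheduled visit. Require at least 4 non-missing scores.
2. Name the Day 1 PP-NRS score as the continuous covariate, and add it to SAP 9.3.
3. Keep the single visit-day score, selected by the SAP 10.1.1 window rule, as a supportive analysis.
4. Confirm that every daily score is entered in the eCRF.

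The exclusions are needed because the Day 8 and Day 15 visits may each fall 3 days either side of target. A Day 8 visit held on Day 5 leaves Days 2–5, exactly 4 mornings; without the exclusion the baseline score would enter its own follow-up value. Visits on Days 11 and 12 would otherwise share six of seven mornings; with the exclusion the later one has a single morning, so the SAP must also say what happens when fewer than 4 scores remain. Week 4 is not affected: the Day 15 visit falls no later than Day 18 and the Day 28 visit no earlier than Day 26, so 7 mornings are always available.

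**Cost.** SAP wording and a short derivation if all diary days are already entered; otherwise extra data entry and possibly an eCRF revision. The value describes average itch over the preceding week, which may dilute a still-growing effect, mainly at Day 8. The supportive single-day analysis would show this.
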